## **9.4.2 Calculation or derivation of efficacy variables**

### **Investigator assessments**

At each visit, patients will be programmatically assigned a response of CR, PR, SD, or PD depending on the status of their disease compared with baseline and previous assessments (by investigator assessment according to RECIST v1.1 criteria). If a patient has had a tumour assessment which cannot be evaluated, then the patient will be assigned a visit response of not evaluable (NE) unless there is any evidence of progression in which case the response will be assigned as PD. Please refer to Appendix C for the definitions of CR, PR, SD, and PD. The investigator assessments will be used in the calculation of PFS, APF12, ORR and DoR.

### **Progression free survival**

Progression-free survival is defined as the time from first dose of study treatment until the date of objective disease progression or death (by any cause in the absence of progression) regardless of whether the patient withdraws from study therapy or receives another anti-cancer therapy prior to progression. Patients who have not progressed or died at the time of analysis will be censored at the time of the latest date of assessment of investigator. However, if the patient progresses or dies after 2 or more missed visits, the patient will be censored at the time of the latest assessment. If the patient has no evaluable visits or does not have baseline data, they will be censored at the day of first dose unless they die within 2 visits of baseline. The PFS time will always be derived based on scan/assessment dates not visit dates.

The following rules will be applied:

- Date of progression will be determined based on the earliest of the dates of the component that triggered the progression.
- When censoring a patient for PFS, the patient will be censored at the latest of the dates contributing to a particular overall visit assessment.

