### **Objective Response Rate**

Objective Response Rate is defined as the number (%) of patients with measurable disease with at least 1 visit response of CR or PR. Data obtained up until progression or last evaluable assessment in the absence of progression will be included in the assessment of ORR. If any patients do not have measurable disease at baseline then the analysis of ORR will exclude these patients, so that the denominator is a subset of the SS who have measurable disease at baseline.

However, any CR or PR which occurred after a further anti-cancer therapy was received will not be included in the numerator for the ORR calculation.

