### **Duration of Response**

Duration of response is only calculated for patients who have a best overall tumor response of CR or PR before subsequent anti-cancer therapy. Duration of response will be defined as the time from the date of first documented response until the date of documented progression or death in the absence of disease progression. The end of response should coincide with the date of progression or death from any cause used for the PFS endpoint. The time of the initial response will be defined as the latest of the dates contributing towards the first visit response of PR or CR.

If a patient does not progress following a response, then his/her duration of response will use the PFS censoring time.

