### **Clinical examination**

Clinical examination will not be used for assessment of TL. Clinically detected lesions can be selected as TLs if they are assessed by CT or MRI scans. Clinical examination can be used to assess NTL and to identify the presence of new lesions.

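### PFS is censored at the latest assessment whether or not it was evaluable, so trailing not-evaluable scans lengthen PFS, APF12 and DoR by a modest amount

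*Protocol*

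**What the plan says.** All of these rules stand in Protocol Section 9.4.2.

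- **PFS, no event.** The patient "will be censored at the time of the latest date of assessment of investigator".
- **PFS, event after a gap.** "if the patient progresses or dies after 2 or more missed visits, the patient will be censored at the time of the latest assessment".
- **PFS, nothing evaluable.** "If the patient has no evaluable visits or does not have baseline data, they will be censored at the day of first dose", with an exception for early death. This is the only PFS rule that refers to evaluability.
- **PFS, which dates count.** "The PFS time will always be derived based on scan/assessment dates not visit dates". A further bullet takes the latest date within the overall visit assessment used for censoring.
- **Visit response.** When a tumour assessment cannot be evaluated, "then the patient will be assigned a visit response of not evaluable (NE"), unless there is evidence of progression, in which case it is PD.
- **ORR.** "Data obtained up until progression or last evaluable assessment in the absence of progression will be included in the assessment of ORR".
- **APF12** is the Kaplan-Meier estimate of PFS at 12 months.
- **DoR.** If a responder does not progress, "then his/her duration of response will use the PFS censoring time".

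**The concern.** An NE scan is an assessment in the protocol's own terms, so read literally it can set the censoring date. Time after the last evaluable scan is then credited as progression-free although the disease status over that time was not established.

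The protocol also treats the same kind of scan in two ways. A patient whose scans are all NE earns no PFS time. A patient with one evaluable scan followed by NE scans earns time up to the last NE scan. No reason is given for the difference, and the ORR paragraph shows that the authors write evaluable when they mean it.

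At stake are the absolute PFS, APF12 and DoR estimates. The trial has a single arm, so no control group carries the same bias and offsets it.

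**Working it through.** **1. Reading the rules together.** Take scans at weeks 6, 12, 20 and 28 (the schedule in the synopsis and Table 2) and no PFS event.

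| Patient | Visit responses | Censored, as written | Censored, last evaluable |
|---|---|---|---|
| A | NE, NE, NE, NE | first dose (0) | first dose (0) |
| B | SD, NE, NE, NE | week 28 (6.4 months) | week 6 (1.4 months) |

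Patient B gains 22 weeks (22 × 7 / 30.44 = 5.1 months) from three scans of a kind that earn patient A nothing.

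The two clarifying sentences in the PFS paragraph do not settle this. An NE scan has a scan date. The latest-contributing-date bullet chooses a date within an assessment, not which assessment to use, and NE is itself an overall visit response in Table 13 (Appendix C).

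**2. Direction.** Kaplan-Meier gives S(t) = ∏(1 − d/n). Keeping a patient in n between the last evaluable scan and a later NE scan, with no event added to d, lowers d/n and raises S(t). APF12 is S(12 months) and DoR takes the PFS censoring time, so both inherit the direction.

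**3. Size.** The protocol gives no figure for NE scans or for their effect on PFS. Its one precision figure, 5.7% for a 60% incidence at n = 300 (Section 9.2), reproduces as 5.69% by Clopper-Pearson but does not bear on this point. The size therefore needs simulation.

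Inputs from the protocol:
- n = 300, with data cut-off 6 months after the last patient enters.
- Scans at weeks 6 and 12, then every 8 weeks.
- PFS median 5.1 months and 17.5% at 12 months (Section 2.2.1.2, the cited phase III study).

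Assumptions not in the protocol:
- Uniform accrual over 15 months.
- NE probability of 2% to 20% per scan, independent between scans.
- Loss to follow-up of 1% or 3% per month.
- NE scans reveal no progression, and all events are found at scans.

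Weibull fit, S(t) = exp[−(t/λ)^k]:
- k = ln[ln(1/0.175)/ln 2] / ln(12/5.1) = ln(2.515)/ln(2.353) = 1.08
- λ = 5.1/(ln 2)^(1/k) = 7.17 months

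Each simulated trial was analysed under both censoring rules, with 150 trials per row. Entries are averages.

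| NE per scan | Loss per month | Patients whose date moves | APF12, any assessment | APF12, evaluable | Difference (points) | Median difference (months) |
|---|---|---|---|---|---|---|
| 2% | 1% | 1.8 | 18.7% | 18.6% | 0.1 | 0.01 |
| 2% | 3% | 2.1 | 17.5% | 17.4% | 0.1 | 0.02 |
| 5% | 1% | 4.2 | 18.5% | 18.3% | 0.2 | 0.01 |
| 5% | 3% | 5.0 | 18.1% | 17.8% | 0.3 | 0.01 |
| 10% | 1% | 8.5 | 19.0% | 18.5% | 0.5 | 0.01 |
| 10% | 3% | 9.5 | 18.9% | 18.3% | 0.6 | 0.05 |
| 20% | 1% | 17.7 | 20.1% | 19.0% | 1.1 | 0.04 |
| 20% | 3% | 19.4 | 19.5% | 18.2% | 1.3 | 0.07 |

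Simulated medians (6.1 to 6.5 months) exceed 5.1 because progression is recorded at the next scan; only the differences matter here. Simulated maturity of 66-76% follows from the assumed accrual and is not a test of the 60% stated in Section 9.5.4. DoR and the missed-visits sentence were not simulated.

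**4. Scale.** The 95% half-width for APF12 at n = 300, ignoring censoring, is 1.96 × √(0.175 × 0.825 / 300) = 4.3 points.

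**The case against.** The strongest reply is that the paragraph already implies a last-evaluable rule. The first-dose sentence is the natural residual case of such a rule, and one missing qualifier could be settled in the SAP. That is a fair account of what was probably intended. It does not remove the point, because the protocol fixes a date. An SAP using the last evaluable assessment would depart from that wording, and one that follows it carries the bias.

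A reader might also infer three stronger things, which the documents do not support.

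- **That any clinic visit extends PFS.** It does not: PFS rests on scan or assessment dates and on dates that feed an overall visit assessment. Appendix C does say "Clinical examination can be used to assess NTL and to identify the presence of new lesions", so an examination of non-target lesions without target-lesion imaging could yield an overall NE. But Appendix C also requires the baseline CT/MRI methods at every follow-up assessment, and such a visit is only another instance of the NE problem.
- **That progression cannot be found at an NE visit.** Section 9.4.2 assigns PD whenever there is evidence of progression. Table 11 lets PD override NE, and Table 13 gives PD for a new lesion or non-target progression whatever the target-lesion status. Death remains an event. NE visits are therefore partly informative, and the simulation, which gives them no information, leans towards overstating the effect at a given rate of scattered NE scans.
- **That APF12 is inflated by several points.** This needs NE scans to cluster heavily. If 5% or 10% of patients had every remaining visit NE, a separate simulation (12-month accrual) gives shifts of 1.9 or 3.8 points. A further check that counts deaths gives about 1.7 or 3.5, falling to about 1.1 or 2.3 if half of progressions are still caught. Nothing in the protocol suggests such a pattern.

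**Conclusion.** The point holds as a wording defect with a known direction and a modest size. Both PFS censoring sentences omit the requirement that the assessment be evaluable, and this is inconsistent with the first-dose rule in the same paragraph and with the ORR rule.

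The upward shift in APF12 is about 0.1 to 0.6 point at NE rates of 2-10% per scan and 1.1 to 1.3 points at 20%, with the median moving by less than 0.1 month. Those shifts are well inside the sampling half-width of about 4.3 points. They rest on the assumed NE rates, accrual and loss to follow-up. For DoR only the direction is established.

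PFS, APF12 and DoR are secondary and descriptive, with no test or decision rule attached, and the primary safety endpoints are untouched. The change is still worth making before the data are analysed, because the bias runs one way and is easily removed.

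**What to change.** Change both sentences in Section 9.4.2, Progression free survival:

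- **No event:** censor at the latest of the dates contributing to the last evaluable RECIST 1.1 overall visit response (CR, PR or SD).
- **Progression or death after two or more missed visits:** censor at that same date. Changing only the no-event sentence would leave two standards in one paragraph.

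Keep the existing first-dose rule, with its early-death exception, for patients with no evaluable visit. DoR already takes the PFS censoring time, so it needs no separate edit beyond using this same date; APF12 follows from PFS.

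The cost is a few words and standard programming, with no new data. PFS, APF12 and DoR will come out slightly less favourable.

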### **Proportion of patients alive and progression free at 12 months**

The APF12 will be defined as the Kaplan-Meier estimate of PFS (per investigator assessment according to RECIST v1.1 criteria) at 12 months.

### **Objective Response Rate**

Objective Response Rate is defined as the number (%) of patients with measurable disease with at least 1 visit response of CR or PR. Data obtained up until progression or last evaluable assessment in the absence of progression will be included in the assessment of ORR. If any patients do not have measurable disease at baseline then the analysis of ORR will exclude these patients, so that the denominator is a subset of the SS who have measurable disease at baseline.

However, any CR or PR which occurred after a further anti-cancer therapy was received will not be included in the numerator for the ORR calculation.

### **Duration of Response**

Duration of response is only calculated for patients who have a best overall tumor response of CR or PR before subsequent anti-cancer therapy. Duration of response will be defined as the time from the date of first documented response until the date of documented progression or death in the absence of disease progression. The end of response should coincide with the date of progression or death from any cause used for the PFS endpoint. The time of the initial response will be defined as the latest of the dates contributing towards the first visit response of PR or CR.

If a patient does not progress following a response, then his/her duration of response will use the PFS censoring time.

### **Overall survival**

Overall survival is defined as the time from the date of first dose of study treatment until death due to any cause. Any patient not known to have died at the time of analysis will be censored based on the last recorded date on which the patient was known to be alive.

### **Proportion of patients alive at 12 months**

The OS12 will be defined as the Kaplan-Meier estimate of OS at 12 months.

## **9.5 Methods for statistical analyses**

Analysis for this study will mostly be descriptive. Continuous variables will be summarised by the number of observations (n), mean, standard deviation (SD), median, quartiles (Q1 and Q3), minimum, and maximum. Categorical variables will be summarised by frequency counts and percentages for each category. Two-sided 95% CIs will be provided as appropriate.

Approximately, 300 patients will be enrolled to this study. All subjects who received at least 1 dose of study treatment will be included in the safety analysis set, which will be the primary analysis set for all analyses.

### 9.5.1 Analysis of the primary variables

One of the primary outcome measures for the study is the frequency and percentage of patients with AEs of CTCAE grade  $\geq 3$ , and it will be summarized by System Organ Class and preferred term. The same summary table will be generated by maximum CTCAE grade and by relationship to the treatment. AEs of CTCAE grade  $\geq 3$  (both in terms of MedDRA preferred terms and CTCAE grade) will be listed individually by patient. The Clopper-Pearson 95% CIs around the incidence rate will also be reported.

Similar analyses will be conducted for imAEs.

### 9.5.2 Analysis of the secondary variables

One of the secondary objectives is to assess the efficacy of first-line durvalumab + EP in terms of PFS, ORR, DoR and OS. PFS (by investigator assessment according to RECIST v1.1 criteria) is defined as the time from first dose of treatment until the date of objective PD or death (by any cause in the absence of progression) regardless of whether the patient withdraws from therapy or receives another anticancer therapy prior to progression. ORR is defined as the percentage of patients with a best response of CR (complete response) or PR (partial response) by investigator assessment according to RECIST v1.1 criteria. DoR will be defined as the time from the date of first documented response until the date of documented progression or death in the absence of disease progression. OS is defined as the time from first dose of treatment until death due to any cause. Time-to-event data (PFS, OS) will be summarized using Kaplan-Meier estimates of the median event time and quartiles together with their 95% CIs, given the anticipated maturity of 60%. The Kaplan-Meier curves will be provided. The proportion of patients alive and progression free at 12 months (APF12), the proportion of patients alive at 12 months (OS12) will be summarized (using the Kaplan-Meier curve). ORR will be summarized descriptively, and the Clopper-Pearson 95% confidence intervals (CIs) will be provided. A median duration of response and associated 95% confidence interval will be calculated for responding patients.

Analyses similar to the primary endpoints will be conducted for overall AEs, SAEs, AESIs and AEs leading to discontinuation of study treatment. In addition, the number and percentage of patients with AEs will be presented by PT. Time to event endpoints will be analysed using Kaplan-Meier estimates of the median event time.

### 9.5.3 Subgroup analysis

Subgroup analysis of safety and efficacy will be conducted for the cohorts of patients with PS 0 to 1 and 2 at baseline. For time to event analysis, each subgroup must have at least 20 events per subgroup level in order for that subgroup level to be included in the subgroup analysis. Additional subgroup analyses may be conducted for safety and efficacy parameters based on the following and will be defined in the SAP as appropriate:

- Platinum received in Cycle 1 (cisplatin versus carboplatin)
- Sex (male versus female)
- Age (<65 versus  $\geq 65$  years of age)

- Smoking status (current versus former versus never smoker)
- Number of cycles of EP ( $\leq 4$  versus  $> 4$ )
- Use of PCI (yes versus no)

Other baseline variables may also be assessed pending clinical justification. The purpose of the subgroup analyses is to assess the consistency of effect across expected prognostic and/or predictive factors. Forest plot(s) will be generated.

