### **2.1.5 Rationale for conducting this study**

ES-SCLC is an aggressive malignancy and the prognosis remains poor despite favorable initial response to platinum-based chemotherapy, which has been the standard treatment for over 3 decades. Recently, immunotherapy targeting the programmed cell death-1 (PD-1) and programmed cell death ligand-1 (PD-L1) pathway has demonstrated clinical activity for patients with ES-SCLC, including as first-line treatment. While the CASPIAN study demonstrated improved OS with the addition of durvalumab to carboplatin or cisplatin plus etoposide (Paz-Ares 2019), there remains unmet needs for improved treatments in first line ES-SCLC in China, particularly more safety data for patients who would not have been included in CASPIAN study, including the ECOG PS=2 population and for those patients for whom flexible number of chemotherapy cycles is important in treatment decision making.

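### The subgroup list treats number of EP cycles and PCI use as baseline factors, so PFS and OS by these groups, if run as listed, would carry guaranteed-time bias

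*Protocol*

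**What the plan says.** Section 9.5.3 commits to one subgroup split, PS 0 to 1 versus 2. It then adds a second tier: "Additional subgroup analyses may be conducted for safety and efficacy parameters based on the following and will be defined in the SAP as appropriate". That list holds platinum in cycle 1, sex, age, smoking status, "Number of cycles of EP" (at most 4 versus more than 4) and "Use of PCI (yes versus no"). The next sentence allows further baseline variables, so the listed ones are treated as baseline too. The aim is to "assess the consistency of effect across expected prognostic and/or predictive factors", and forest plots are promised. The only condition on time-to-event subgroups is that "each subgroup must have at least 20 events per subgroup level".

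Under Section 9.4.2, "Progression-free survival is defined as the time from first dose of study treatment until the date of objective disease progression or death". OS also starts at first dose. The synopsis (duration of treatment) leaves 4 to 6 EP cycles to the investigator during treatment, and its study design paragraph leaves PCI to the investigator's discretion.

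**The concern.** A subgroup factor for a time-to-event endpoint should be known when the clock starts. These two are not. Patients who die or stop EP before cycle 5 fall into the lower-cycle group, whatever had been intended for them. Patients with an event before PCI could be given fall into the no-PCI group. The other groups collect only patients who lasted long enough to enter them.

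The protocol handles a similar factor correctly: platinum agent is fixed as the one received in cycle 1, although Section 7.9.2 allows a later switch. Cycles and PCI get no such anchor. The 20-event rule addresses precision and does nothing about bias.

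Readers will look for the cycle contrast, because Section 2.1.5 gives as part of the rationale patients for whom a "flexible number of chemotherapy cycles is important in treatment decision making".

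**Working it through.** The protocol gives no figure for these subgroups, so there is none to reproduce. Its precision figures in Section 9.2 (5.7% and 4.7% at n = 300) recompute as 5.69% and 4.68%. They concern overall incidence and are not in question.

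**Inputs from the protocol**
- Cycles last 21 days (Table 2) and doses are at least 21 days apart (Section 5). Cycle 5 therefore starts no earlier than 4 × 21 = 84 days, or 84/30.4375 = 2.76 months, after first dose.
- Median PFS is 5.1 months and median OS 13.0 months in the durvalumab + EP arm of the earlier phase III trial (Section 2.2.1.2).

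**Assumptions, not in the documents**
- Event times are exponential.
- A share q of patients is intended for more than 4 cycles, independently of prognosis; q = 30, 50 or 70%.
- EP stops at the PFS event (relaxed below).
- Cycle number has no effect on outcome.

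**Who can reach cycle 5.** λ = ln 2/5.1 = 0.1359 per month and S(84 days) = exp(−0.1359 × 2.76) = 0.687, so 31% have a PFS event first. For OS, exp(−(ln 2/13.0) × 2.76) = 0.863, so 14% die first.

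**PFS by cycles.** The group with more than 4 cycles is a fraction p = 0.687q of patients, with median 2.76 + 5.1 = 7.9 months. In the other group, survival is (1 − q)S(t)/(1 − p) after day 84 and (S(t) − p)/(1 − p) before it; setting this to 0.5 gives the median. Mean PFS is 1/λ = 7.36 months overall, 2.76 + 7.36 = 10.12 with more than 4 cycles, and (7.36 − 10.12p)/(1 − p) otherwise. The rate ratio is the last mean divided by 10.12.

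| q | p | Median, >4 | Median, ≤4 | Rate ratio |
|---|---|---|---|---|
| 30% | 0.206 | 7.9 | 4.2 | 0.66 |
| 50% | 0.344 | 7.9 | 3.1 | 0.58 |
| 70% | 0.481 | 7.9 | 2.2 | 0.47 |

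At q = 50%, 12-month PFS is 0.1957/0.6872 = 28% versus 0.5 × 0.1957/0.6564 = 15%.

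**OS by cycles.** The same formulas give 2.76 + 13.0 = 15.8 months versus about 11.9, 10.6 and 7.8 months for q = 30, 50 and 70%.

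**EP continued past the PFS event.** With a 28-day lag a patient need only be event-free at day 56 (1.84 months, S = 0.779). At q = 50% the medians are 1.84 + 5.1 = 6.9 versus 3.6 months, rate ratio 0.67. The lag is applied to deaths as well, which is a simplification.

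**PCI.** Replace day 84 by an assumed PCI start.
- Month 3, 10% use: p = 0.067, ratio (7.36 − 0.067 × 10.36)/0.933/10.36 = 0.69.
- Month 5, 50% use: p = 0.253, ratio (7.36 − 0.253 × 12.36)/0.747/12.36 = 0.46.

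**Safety.** AEs count until 90 days after durvalumab stops (Section 9.4.1), so the window differs between patients. Take one Grade ≥3 hazard h for everyone and a window running to the PFS event plus 3 months. Setting 1 − exp(−3h) × λ/(λ + h) = 60% overall gives h = 0.109 per month. Then:
- More than 4 cycles: 1 − exp(−5.76h) × λ/(λ + h) = 70%.
- At most 4 cycles: (0.60 − 0.704p)/(1 − p) = 57, 55 and 50%.

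If half of the patients with an early AE stop EP, simulation narrows this to about 66% versus 59 to 56%. Exposure and toxicity-driven stopping pull in opposite directions.

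**Does a landmark remove the bias?** In null simulations with 300 patients, a day-84 landmark brought the hazard ratio for more than 4 versus at most 4 cycles to 0.99–1.04 (PFS) and 0.99–1.01 (OS), with 3 to 6% false positives. For PCI, with the landmark at its assumed start, it was 0.97–1.01 with 3 to 7%.

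**The case against.** The strongest reply is that these analyses are optional. The protocol says they may be done and leaves their definition to the SAP, which is not at hand and could specify a landmark. That is a fair limit on severity. It does not remove the point, because the protocol itself fixes the factors, the cycle cut-point, the baseline framing and the forest plots.

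Second, the trial is single-arm and mostly descriptive, and no between-group test or hazard ratio is specified. That is also true, but side-by-side Kaplan-Meier medians carry the same distortion without a test.

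Third, Section 8.2.1 and Appendix C allow treatment past initial RECIST progression, so progression near week 12 need not prevent cycle 5. This stands and makes the PFS bias smaller, as shown. It does not help OS, since a patient must be alive to receive cycle 5.

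Three stronger readings are tempting but not supported:
- A reader might infer that safety by cycle number suffers from immortal time and cannot be interpreted. AE incidence by cycles received is a legitimate exposure description if labelled as one; the trouble is unequal exposure and toxicity shortening EP, with no fixed net direction.
- A reader might infer that the trial's main results are compromised. The overall estimates and the PS split do not use these factors.
- A reader might assume that PCI requires completed chemotherapy. The protocol says only that it is at the investigator's discretion under standard-of-care guidance, so its timing is an assumption here.

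**Conclusion.** The point holds as a fault in how two optional secondary subgroups are set up. Run as listed, PFS and OS would favour more than 4 cycles and PCI when neither has any effect. For cycles the null PFS rate ratio is about 0.66 to 0.47 over 30 to 70% intended use, and 0.67 at 50% use with a 28-day lag. For PCI it is about 0.69 to 0.46 over 10 to 50% use at months 3 to 5. These sizes rest on exponential event times and on use rates and PCI timing that the documents do not give. The direction was the same in every PFS and OS setting tried.

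**What to change.** Remove both factors from the baseline subgroup list and the forest plots in Section 9.5.3. If they are still analysed, label them post-baseline and descriptive, and state the method:

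- **PFS and OS by cycles:** use a stated landmark, for example day 84, among patients event-free at that point (alive, for OS). Time runs from the landmark and patients are grouped by EP received afterwards. If cycle 5 is often delayed, some guaranteed time remains; a time-dependent covariate avoids this.
- **PCI:** use a landmark at its start window, or a time-dependent covariate.
- **Safety:** report AE rates per patient-time or per cycle received. Do not restrict to AEs starting after week 18: six cycles take 6 × 21 = 126 days, so that would discard the on-schedule chemotherapy-period events, including those of cycles 5 and 6.

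Neither method removes selection by the investigator, so the descriptive label stays. The cost is protocol and SAP wording, some programming and fewer patients in the landmark analyses: about 69% progression-free at day 84 under the exponential assumption, or 0.687 × 300 = 206. Trial conduct does not change.
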